5.3.1.3 Change and Percentage Change from Baseline

Change from baseline will be calculated as:

$$\text{Change from baseline} = \text{value at timepoint} - \text{baseline value}$$

Change from baseline will be presented to the same level of precision as the original value in the listings.

Percentage change from baseline will be calculated as:

$$\text{Percentage change from baseline} = 100 * (\text{change from baseline} / \text{baseline value})$$

Percentage change from baseline will be presented to 1 decimal place (dp) in the listings.

5.3.2 Demographic and Background Data

Height may be recorded in cm or inches. Height in inches will be converted to height in cm as follows:

$$\text{Height (cm)} = \text{Height (inches)} * 0.3937$$

Height (cm) will be presented to 1 dp in the listings.

Weight may be recorded in kg or pounds. Weight in pounds will be converted to weight in kg as follows:

$$\text{Weight (kg)} = \text{Weight (pounds)} * 0.4536$$

Weight (kg) will be presented to 1 dp in the listings.

Body mass index (BMI) will be calculated as:

$$\text{BMI (kg/m}^2\text{)} = \text{Weight (kg)} / [\text{height (cm)}/100]^2$$

BMI (kg/m²) will be presented to 1 dp in the listings.

5.3.2.1 Study Drug Compliance

Participants in groups 1 and 2 will be expected to dose once daily with 2 capsules per dose (2 capsules per day); in group 3 – once daily with 1 capsule.

Compliance will be calculated across the whole treatment period in this study.

Expected capsules for the treatment period for groups 1 and 2 will be calculated as:

$$\text{Expected capsules} = 2 * (\text{End date of treatment period} - \text{Start date of treatment period} + 1).$$

Expected capsules for the treatment period for group 3 will be calculated as:

$$\text{Expected capsules} = \text{End date of treatment period} - \text{Start date of treatment period} + 1.$$

End date of treatment period = Date of the last dose of study drug.

Start date of treatment period = Day 1.

Actual capsules taken will be calculated from the dosing log using entries between the start and end days inclusively.

Study drug compliance will be calculated as:

$$\text{Study drug compliance (\%)} = 100 * \text{Actual capsules taken} / \text{Expected capsules taken}.$$

Study drug compliance will also be categorized as:

- <80%
- ≥80%

5.3.2.2 Emollient Compliance

All participants must use an emollient twice daily until the Week 40 Follow-up Visit.

Compliance will be calculated across the whole treatment period and follow-up period in this study.

Expected number of applications for the treatment + follow-up period will be calculated as:

$$\text{Expected number of applications} = 2 * (\text{End date of period} - \text{Start date of period} + 1).$$

End date of period = End of study day. Start date of period = Day 1.

Actual number of applications will be calculated from the emollient usage diary using entries between the start and end days inclusively. In case of more than two applications per day participant will be considered compliant for that day and only two applications will be considered for compliance calculation.

Emollient compliance will be calculated as:

$$\text{Emollient compliance (\%)} = 100 * \frac{\text{Actual number of applications}}{\text{Expected number of applications}}$$

Emollient compliance will also be categorized as:

- <75%
- ≥75%

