7.4. Early Termination Visit

Participants who withdraw prematurely from the study should have an early termination visit using the Early Termination Visit schedule within 14 days of asking to withdraw consent or within 72 hours of starting any AD therapy if their withdrawal was due to treatment failure. The Early Termination Visit will consist of the same assessments and procedures as the End of Treatment Study Visit at Week 36. Once all assessments are complete, study staff will assist the participant to uninstall the mobile application from their smartphone device. The participant will also be asked to have a final telephone call 28 days (+3 days) after taking their last dose of IMP for safety assessments. The date of this telephone call will be considered the end of study date for these participants.

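### Emollient compliance is understated for early terminators because the expected-application period runs past the removal of the eDiary

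*SAP*

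**What the plan says.** SAP 5.3.2.2 defines expected applications as twice the number of days in the period, with "End date of period = End of study day. Start date of period = Day 1". The numerator has one source: "Actual number of applications will be calculated from the emollient usage diary using entries between the start and end days inclusively". Days with heavier use are capped: "only two applications will be considered for compliance calculation". The percentage is then split at 75%.

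The SAP does not define end of study day further. Protocol 7.4, repeated in footnote o of Table 4-1, does so for participants who withdraw early. They have a "final telephone call 28 days (+3 days) after taking their last dose of IMP", and "The date of this telephone call will be considered the end of study date for these participants". The same section deals with the diary at the earlier visit: "Once all assessments are complete, study staff will assist the participant to uninstall the mobile application from their smartphone device". Protocol 6.6.1 agrees: at the Week 40 or Early Termination Visit the application is removed and any issued device is collected.

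**The concern.** For an early terminator, the denominator runs to the call but the numerator stops at the visit. The call is for safety assessments, and no other record of emollient use enters the formula. Because of the daily cap, extra applications earlier on cannot make up the shortfall.

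Completers do not have this problem, since their diary and their study participation both end at the Week 40 visit. The bias therefore follows early termination and always runs downwards. Emollient is required background therapy, so the summary could show early stoppers as poor users of it purely because of the visit schedule. SAP 5.3.2.1 avoids the equivalent problem for study drug by ending that period at the last dose, which suggests an oversight here.

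**Working it through.** The documents give no worked compliance figure to reproduce, so the SAP formula is applied directly.

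**Inputs**
- L = study day of last dose, with Day 1 as the start (SAP 5.3.2.2).
- c = days from last dose to the call, 28 to 31 (Protocol 7.4).
- g = days from last dose to the Early Termination Visit, taken as the last diary day. Protocol 7.4 ties the visit to the withdrawal request (within 14 days) or to the start of new AD therapy (within 72 hours), not to last dose. So g is an assumption, shown here for 0, 3, 7 and 14 days.
- u = the participant's true proportion of the two daily applications, capped at 1.

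**Formula**

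Compliance = 100 × 2u(L + g) / [2(L + c)] = 100 × u(L + g)/(L + c).

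Check: a perfect completer with the diary kept to Day 280 scores 2×280/(2×280) = 100%.

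**Perfect user (u = 1), visit on the last-dose day (g = 0), call at +28**

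| Last dose | Calculation | Score |
|---|---|---|
| Day 28 | 28/56 | 50.0% |
| Day 56 | 56/84 | 66.7% |
| Day 83 | 83/111 | 74.8% |
| Day 84 | 84/112 | 75.0% |
| Day 112 | 112/140 | 80.0% |
| Day 168 | 168/196 | 85.7% |
| Day 251 | 251/279 | 90.0% |

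**When a perfect user falls below 75%**

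(L + g)/(L + c) < 0.75 rearranges to L < 3c − 4g.

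| Gap g | Call at +28 | Call at +31 |
|---|---|---|
| 0 days | L < 84 | L < 93 |
| 3 days | L < 72 | L < 81 |
| 7 days | L < 56 | L < 65 |
| 14 days | L < 28 | L < 37 |

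If both applications on the visit day also go unrecorded, each limit moves about 4 days later.

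**Users who are truly at or above 75% but not perfect (call at +28)**

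u(L + g)/(L + c) < 0.75 rearranges to L < (0.75c − ug)/(u − 0.75).
- u = 0.90, g = 0: 21/0.15 = 140, so misclassified for L < 140.
- u = 0.80, g = 0: 21/0.05 = 420, so misclassified at every early stop. For example, 0.80 × 168/196 = 68.6% at Day 168, and 0.80 × 251/279 = 72.0% at Day 251.
- u = 0.80, g = 14: (21 − 11.2)/0.05 = 196, so misclassified for L < 196.

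Put the other way, with g = 0 and call at +28, the true use needed to be scored 75% is 75 × (L + 28)/L. That is 93.8% for a stop at Day 112, 87.5% at Day 168 and 83.4% at Day 251.

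**After correction**

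Ending the period at the Early Termination Visit gives (L + g)/(L + g), so a perfect user scores 100% at any L and g.

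**The case against.** The strongest case against accepts the mismatch but holds that it matters little. Most of that stands.

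- **Reach of the misclassification.** A reader might infer that any perfect user who stops early lands below 75%, or that the split is wrong for every early terminator. Neither follows. A perfect user stopping at Day 168 scores 85.7% with g = 0 and stays in the upper category. The percentage is too low whenever the visit precedes the call, but the category changes only for some participants. Those lost to follow-up may have neither visit nor call, and the calculation does not cover them.
- **Estimands.** Protocol 11.5 lists non-compliant emollient use among deviations accounted for as intercurrent events, so a reader might infer that the error reaches the primary or efficacy results. It does not. Such deviations are handled by treatment policy (Protocol 11.3.1 and 11.3.2; SAP Tables 1 to 3), and no data point set or responder rule uses the emollient percentage or the 75% cut. Protocol 6.9.1.1 also says that missed emollient applications are not protocol deviations.
- **Early termination of the study.** A reader might infer that stopping the study makes the problem larger. The documents give no count of early terminators. SAP Table 9 says only reduced disposition, demography and safety outputs will be produced, and Table 14.1.6 and Listing 16.2.5.4 are both flagged No for early stop. One loose end remains: the opening sentence of SAP 16.1 says study population outputs are produced as planned if the study stops early, which conflicts with the No flag on Table 14.1.6.
- **The cut-offs rest on an assumed gap.** This is correct, so they are given as a range. The direction of the bias does not depend on the gap, provided the visit comes before the call.

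**Conclusion.** The derivation is wrong as written for early terminators whose Early Termination Visit precedes the call: their emollient compliance is understated. Over the gaps examined, a perfect user is put below 75% when the last dose is before Day 84 to 93 (visit on the last-dose day) and, at the other end, before Day 28 to 37 (visit 14 days later). Users between 75% and 100% can be misclassified at later stops, up to any early stop for an 80% user with g = 0. These figures assume that the diary ends on the visit day and that the call falls 28 to 31 days after last dose.

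The consequence is limited to one descriptive table and one listing in the full package. Severity is minor.

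**What to change.** In SAP 5.3.2.2, define the end date of the period as the earlier of the end of study date and the date of the Week 40 or Early Termination Visit; if neither visit occurred, use the last day the eDiary was available. The fallback should rest on availability of the diary rather than on the last entry made, since ending at the last entry would discard real days of non-use. Apply the same date in Table 14.1.6 and Listing 16.2.5.4.

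While editing, reconcile the opening sentence of SAP 16.1 with the early-stop flag on Table 14.1.6, so that it is clear whether the table is produced.

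The cost is one line of SAP text and one derivation change. No new data are needed.

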5.3.2.3 Prohibited Concomitant Medications

Use of any of the following concomitant medications during the study require the IMP to be immediately discontinued where possible. If a participant requires treatment for atopic dermatitis with a prohibited concomitant medication during the study, they will be classified as a treatment failure:

- Topical Corticosteroids (TCS) or Topical Calcineurin Inhibitors (TCI) (unless considered a rescue therapy)
- Topical Phosphodiesterase (PDE) - 4 Inhibitors
- Topical Janus Kinase (JAK) Inhibitors
- Bleach baths
- Phototherapy treatment
- Tanning beds
- Systemic treatments that may lead to clinical improvements in atopic dermatitis, e.g., oral or injectable corticosteroids, methotrexate, azathioprine, cyclosporine, mycophenolate mofetil, JAK-inhibitors, biologic therapy, and other systemic immunosuppressive therapy (note single dose intra-articular or intra-lesional corticosteroid therapy is permitted)
- Leukotriene Receptor Antagonists
- Allergen Immunotherapy
- Live (attenuated) vaccinations

If a prohibited medication is found to have been used, this will be captured into the protocol deviations log.

Prohibited medications will be identified by the sponsor in a separate spreadsheet. In the EDP1815-207 study, prohibited concomitant medications were categorized into two types. Type 1 prohibited medications did not require study withdrawal and as intercurrent events are equivalent to TCS/TCI rescue therapies; Type 2 prohibited medications are equivalent to the prohibited medications in this study.

5.3.3 Efficacy

5.3.3.1 Eczema Area and Severity Index (EASI)

The Eczema Area and Severity Index (EASI) will be calculated within the [REDACTED] system and taken directly from the supplied data. EASI score ranges from 0 to 72 and combines the individual scores from the four individual body regions of head and neck, upper limbs, trunk, lower limbs. Head and neck body region score ranges from 0 to 7.2, upper limbs – from 0 to 14.4, trunk – from 0 to 21.6, lower limbs – from 0 to 28.8. Further information on the scoring of the EASI is provided in [Section 17](#).

EASI-50, EASI-75 and EASI-90 responses are defined respectively by at least a 50%, 75% and 90% decrease from Baseline in the EASI score.

Sustained EASI-50 response is defined as one which is present at consecutive visits spanning at least 8 weeks in the absence of rescue medication. The sustained response is considered to have been first achieved at the first of the consecutive visits.

5.3.3.2 The Percent of Body Surface Area Involvement (BSA)

The Body Surface Area (BSA) will be calculated as part of EASI score in the [REDACTED] system and taken directly from the supplied data. The percent of BSA involvement will be estimated for each participant, where 1% is approximately the area of the participant's handprint.

BSA-50 and BSA-75 responses are defined respectively by at least a 50% and 75% reduction from Baseline in the BSA.

5.3.3.3 Validated Investigator's Global Assessment (vIGA)

The Validated Investigator Global Assessment scale for Atopic Dermatitis (vIGA) will be calculated within the [REDACTED] system and taken directly from the supplied data. There is a standardized grading system based on an overall assessment of the degree of erythema, papulation/induration, lichenification, and oozing/crusting. In indeterminate cases, extent will be used to differentiate between scores – but otherwise extent is not used in the scoring system. The vIGA score ranges from 0 (Clear skin) to 4 (Severe disease).

5.3.3.4 SCORing Atopic Dermatitis (SCORAD)

The SCORing Atopic Dermatitis (SCORAD) will be calculated within the [REDACTED] system and taken directly from the supplied data. There is an investigator-rated area score which uses the rule of nines to assess disease extent, and a disease intensity score comprising erythema, swelling, oozing/crusting, excoriation, lichenification, and dryness. Additionally, there is a subjective symptoms component which considers itch and sleeplessness scored using a visual analogue scale. These scores combine to give a SCORAD score between 0 and 103.

SCORAD-35, SCORAD-50 and SCORAD-75 responses are defined respectively by at least a 35%, 50% and 75% reduction from Baseline in the SCORAD score.

5.3.3.5 Patient Oriented Eczema Measure (POEM)

The Patient Oriented Eczema Measure (POEM) will be calculated within the [REDACTED] and taken directly from the supplied data. It includes a series of 7 questions, measuring itch, sleep, bleeding, weeping/oozing, cracking, flaking, and dryness/roughness over the last week, and is scored by the participant. Each of the 7 questions is scored from 0 (no days) to 4 (every day), giving a POEM score range from 0 to 28, with higher scores representing higher disease severity.

POEM response is defined as a reduction of ≥ 4 in the POEM score if a participant has a score of ≥ 4 at baseline.

5.3.3.6 Dermatology Life Quality Index (DLQI)

The DLQI is a 10-item questionnaire with each item scored from 0 to 3.

The DLQI score is the sum of the 10 individual items and ranges from 0 to 30, with higher scores indicating greater impairment of quality of life. Further information on the scoring of the DLQI is provided in [Section 21](#).

DLQI response is defined as a reduction of ≥ 4 in the DLQI score if a participant has a score of ≥ 4 at baseline (a 4-point change from baseline is considered the minimal clinically important difference threshold).

5.3.3.7 Peak Pruritus Numerical Rating Scale (PP-NRS)

The Peak Pruritus Numerical Rating Scale (PP-NRS) is a scale from 0 to 10 for participants to rate their worst itch that they have experienced over the previous 24 hours. The PP-NRS will be completed daily via a daily questionnaire from the Day-1 visit to the week 40 visit.

PP-NRS score at each visit is calculated as the mean itch daily score for the 7 days prior to and including the visit date. At least 4 daily scores must be available for the score at the relevant visit to be considered evaluable.

PP-NRS responses are defined as a reduction of ≥ 2 and ≥ 4 in the PP-NRS score if a participant has a score of ≥ 2 and ≥ 4 , respectively, at baseline (a ≥ 2 -4-point change from baseline is considered the minimal clinically important difference threshold).

5.3.3.8 Sleep Disturbance Numerical Rating Scale (SD-NRS)

The Sleep Disturbance Numerical Rating Scale (SD-NRS) is a scale from 0 to 10 for participants to rate their worst sleep that they have experienced over the previous 24 hours. The SD-NRS will be completed daily via a daily questionnaire from the Day-1 visit to the week 40 visit.

SD-NRS score at each visit is calculated as the mean sleep daily score for the 7 days prior to and including the visit date. At least 4 daily scores must be available for the score at the relevant visit to be considered evaluable.

SD-NRS response is defined as a reduction of ≥ 2 in the SD-NRS score if a participant has a score of ≥ 2 at baseline (a 2-point change from baseline is considered the minimal clinically important difference threshold).

5.3.3.9 Atopic Dermatitis Control Tool (ADCT)

The Atopic Dermatitis Control Tool (ADCT) is a 6-question PRO instrument used to detect change of disease activity in a person over time. There are six main areas that assess the multi-dimensional aspects of disease control over the course of a week, scored between 0-4. ADCT scores range from a minimum score of 0 and a maximum score of 24. A higher score indicates lower AD control.

5.3.3.10 Rescue Therapy

Rescue therapy use is allowed throughout the entire study: selected topical corticosteroids and calcineurin inhibitors, systemic antimicrobials and topical antibacterial may be prescribed. An unscheduled visit will be performed to collect the assessments prior to administering any rescue therapy, if needed.

Rescue therapy use will be documented as concomitant medication once prescribed and in a daily symptom diary during the whole course. Each rescue therapy course will be recorded in concomitant medication CRF separately, resulting in a one record in a concomitant medication dataset for each course.

Any medications taken during the study and classified as TSC/TCI rescue therapy medications in the sponsor provided spreadsheet will be considered as rescue therapy with exception for medications which stopped at least 14 days before Day 1.

The number of courses of TCS/TCI rescue therapy will be evaluated for two periods: the period beginning with the first dose of active IMP in this study and the period beginning with the first dose of active IMP across this study and the parent study up to the end of treatment. Rescue therapy course will only be counted at the start day of course. If the rescue therapy course starts in one period and continues to the next period it will be counted only in the first period where the start of the course belongs.

5.3.4 Safety

5.3.4.1 Duration of Exposure

The duration of exposure in this study will be calculated as

$$\text{Duration of exposure (days)} = \text{Treatment stop date in 208} - \text{Treatment start date in 208} + 1$$

The duration of active exposure in this and parent study will be calculated as

$$\text{Duration of exposure (days)} = \text{Treatment stop date in 208} - \text{Active treatment start date}^* + 1$$

*If patient received active treatment in parent study, then consider the start date of active treatment from parent study, otherwise, start of treatment in 208.

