4. STUDY DESIGN

4.1. Study Description

This is an Open-Label Extension, multicenter study to evaluate the long-term safety, tolerability, and efficacy of EDP1815 in participants with mild, moderate, and severe atopic dermatitis. Participants who have completed the 16-week treatment period in the EDP1815-207 parent study may be eligible to enroll in this study.

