5.1. Inclusion criteria

To be eligible to participate in this study, all the following criteria must be met:

1. Must have given written informed consent (signed and dated) and any authorizations required by local law and be able to comply with all study requirements.
2. Must have completed the treatment period in a parent study of EDP1815 in the treatment of atopic dermatitis and complied with the protocol to the satisfaction of the investigator
3. All participants must agree to continue the use of a bland additive-free, sodium lauryl sulfate (SLS)-free, and fragrance-free emollient cream, gel, or ointment at least twice daily (or more, as needed) throughout the study.
4. Continue to meet the following contraception criteria:
 - i. Male participants:
 - i. A male participant must agree to use contraception during their participation in this study and for a period of 90 days after the last dose and refrain from donating sperm during this period.
 - ii. Female participants:
 - i. A female participant is eligible to participate if she is not pregnant, not breastfeeding, and at least 1 of the following conditions applies:
 1. Not a WOCBP or
 2. A WOCBP who continues to follow the contraceptive guidance provided in the parent study during participation in this study, including (if applicable) 7 days prior to the first dose, and for at least 1 complete menstrual cycle (≥ 30 days) after the last dose.

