7.1. Day -1 Visit

The Day -1 visit may occur either the same day as the final treatment visit for the parent study, or within 7 days of completing the treatment period of the parent study. If a participant's Day-1 Visit occurs on the same day as the end of treatment visit of the parent study, then any study assessments performed at the final treatment visit of the parent study do not need to be repeated ([See Table 4-1](#)).

Each site will sequentially assign a unique identifier to each participant that will be used for the duration of the study.

On the day of the visit the participant will be asked to withhold the application of the emollient, and where safe, sunscreen and any other topical products until after all study assessments have been performed ([Section 6.9.1.1 Background Therapy](#)).

The following procedures will be performed on the Day -1 Visit:

- Obtain written informed consent from participant
- Assessment of inclusion and exclusion criteria
- Collection of demographics including year of birth, age, gender, race, and ethnicity
- Review of changes in medical history and smoking status from the baseline visit of the parent study
- Full physical examination
- Vital signs (blood pressure, heart rate, respiratory rate, and temperature) including height and weight measurements BMI will be calculated using the participant's height and weight.
- 12-lead electrocardiogram (ECG)
- Blood sample collection for safety labs
- Urine sample collection for pregnancy testing for women of childbearing potential (WOCBP), and for urinalysis
- AD rating scales - vIGA, EASI, BSA, and SCORAD
- Patient reported clinical rating scales – POEM, DLQI and ADCT
- PP-NRS and SD-NRS scores in participant diary

- Digital photographs of the upper and lower body (anterior and posterior) as half body shots. Additional photographs of up to six specific body areas, i.e., limbs, trunk and back (excluding scalp, genitals, and any identifying features) may also be taken
- Review and document concomitant medications and therapies
- Assess and document adverse events (AEs) that occur after participant signs informed consent form (ICF)

The participant will be instructed by the investigator or study staff to continue to use their emollient as per protocol requirements.

Enrollment Procedures

- Enroll the participant in IRT after all Day -1 activities are completed and the participant is still deemed eligible to participate.

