11.2.1. Participant Analysis Sets

Enrolled set: The enrolled set will consist of all participants who sign the ICF.

Full analysis set (FAS): The FAS set will consist of all participants who receive any IMP under this protocol.

Other parent study specific analysis sets may also be used in interim analyses which will be defined by the subset of participants from the FAS who were previously enrolled from the specified parent study or studies.

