7.1.2.2 Data Point Set 2 (DPS2)

DPS2 consists of all observed data collected following the first dose of active IMP, either in the parent study or in this study until 30 days after the last dose of IMP in this study.

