7.4.3 Planned Schedule of Deliveries

The interim and final analyses will be performed throughout the life cycle of the study as required.

At a minimum, there will be EDP1815-207 parent-study specific analysis performed after all participants from

- 207 cohorts 1-3 (Delivery 1)
- 207 cohort 4 (Delivery 2)

have completed this study.

Analysis will be restricted to participants from the corresponding cohorts in the parent study who transitioned to this study.

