9.2.1 Estimands

The primary safety estimands will use the FAS or the parent study specific FAS for the study/cohort specific analysis.

Treatment condition: actual treatment received will be considered.

Population summary measure of interest:

- For the endpoints looking at the period defined by this study only - the incidence and rate per 100 patient-years of each category of TEAEs (DPS1)
- For the endpoints looking at the period defined since first dose of the active IMP in this study and the relevant parent study - the rate per 100 patient-years of each category of TEAEs by treatment group (DPS2)

Intercurrent events will be accounted for in the following manner:

Table 1: Intercurrent Event Strategies of the Primary Estimand

Discontinuation of treatment	The use of prohibited medications or TCS/TCI rescue therapy, non-compliance with study drug, and any deviations from protocol
Composite strategy Only events which start within 30 days after discontinuation of treatment (TEAEs) will be included in the assessments of incidences and rates	Treatment policy strategy: Data will be used as collected

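### Do the rates of fatal TEAEs and TEAEs causing discontinuation need a different denominator in the combined parent-plus-extension period?

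*SAP*

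**What the plan says.** SAP 9.2 defines two primary safety periods. One starts at the first dose in 208. The other starts at the first active dose in either study (DPS2) and runs "until 30 days after the last dose of IMP in this study". For the combined period, Protocol 11.3.1 and SAP 9.2.1 name the rate per 100 patient-years, by treatment group, as the summary measure. It applies to twelve TEAE categories, including fatal events, events causing discontinuation of study drug, and the drug-related version of each.

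SAP 5.3.4.1 gives the only exposure definition for this period: "If patient received active treatment in parent study, then consider the start date of active treatment from parent study". Exposure ends at the 208 stop date.

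Four statements fix who is counted:

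- Protocol 5.1: "Must have completed the treatment period in a parent study of EDP1815 in the treatment of atopic dermatitis".
- Protocol 4.1, on who may be eligible: "Participants who have completed the 16-week treatment period in the EDP1815-207 parent study".
- Protocol 11.2.1: "The FAS set will consist of all participants who receive any IMP under this protocol".
- SAP 7.4.3: "Analysis will be restricted to participants from the corresponding cohorts in the parent study who transitioned to this study".

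The last two rows of SAP Table 9 record early termination and a reduced output package. SAP 9.1 and 11.1 restrict early-stop safety reporting to the 208 period, and SAP 9.1 restricts it to incidence and number of events.

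**The concern.** This is immortal person-time. Anyone who died during 207, or left before finishing its treatment period, is not in the analysis set, yet the parent-study days of those who did continue enter the denominator. A death rate over that time is low by construction. The same applies to discontinuation if completing 207 treatment meant staying on drug.

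The dilution would also be uneven. Participants on placebo in the parent study add no parent time. The column for those who moved from 6.4×10¹¹ to 1.6×10¹¹ cells per day (the switch column) is entirely parent-active, while the 1.6×10¹¹ and 6.4×10¹¹ columns also hold parent-placebo participants. At equal true risk the switch column would look safest. At stake would be a primary safety rate that flatters the drug and a misleading contrast between columns.

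**Working it through.** **Inputs**

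- Parent treatment: 16 weeks = 112 days (Protocol 4.1).
- 208 treatment: T = 36 weeks = 252 days (Protocol 4.2).
- Gap between studies: 0 to 7 days. Day -1 may fall on the last parent treatment visit "or within 7 days of completing the treatment period of the parent study" (Protocol 7.1).
- Event window after last dose: 30 days (SAP 7.1.2.2).
- Parent-active share of a column, p: not given in the documents. It is 1 in the switch column by definition; 0.75 and 0.5 are assumed for illustration.
- Denominator: SAP 5.3.4.1 exposure. This is inferred, because the SAP does not say which patient-years the rates use.
- Constant hazard and full 208 treatment are assumed.

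**The plan's own figure.** 112 + 252 = 364 days, which matches the top combined-exposure category in SAP 11.2 (52 weeks).

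**Planned rate as a fraction of the rate over time at risk in 208**

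| | Formula | p = 1 | p = 0.75 | p = 0.5 |
|---|---|---|---|---|
| Discontinuation | 252/(252 + 112p) | 0.692 | 0.750 | 0.818 |
| Fatal, exposure ends at last dose | (252 + 30)/(252 + 112p) | 0.775 | 0.839 | 0.916 |
| Fatal, 30 days added to denominator | 282/(282 + 112p) | 0.716 | 0.770 | 0.834 |

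With a 7-day gap the discontinuation figure at p = 1 is 252/371 = 0.679. Shorter 208 exposure deepens it: 168/280 = 0.600 and 112/224 = 0.500.

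**Between columns.** For discontinuation, the switch column relative to a column with share p is (252 + 112p)/364: 336/364 = 0.923 at p = 0.75 and 308/364 = 0.846 at p = 0.5. It would look 8% to 15% better at equal risk.

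**Offset from parent-onset events.** SAP 5.3.4.2 classifies TEAEs by onset, and AEs ongoing from the parent study are followed in 208 (Protocol 9.4). An AE that began in 207 and caused a stop in 208 therefore counts in DPS2. If such events add a fraction k to the stops, the factor at p = 1 is (1 + k) × 252/364: 0.762 at k = 0.1, 0.831 at k = 0.2, and 1 at k = 112/252 = 0.444. The documents do not bound k.

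**What will be produced.** In SAP 16.3.1 the combined-period overview (14.3.1.1.2) and every other DPS2 safety table are marked No in the Early Stop column. The retained tables by system organ class and preferred term carry a note to drop the rate, and SAP 9.1 limits the primary summary to incidence and counts. No figure with this denominator is reported.

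**Whether a simple substitution would work.** Replacing the combined-period rate with the 208-only rate fails. The 208-only tables have three dose groups and no switch column, and their numerator leaves out parent-onset events, so the rate would not match the combined-period counts beside it. Extending patient-years to 30 days after last dose for every category adds time in which drug can no longer be discontinued: 252/282 = 0.89 of the at-risk value.

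**The case for a change.** The strongest argument for a change is that the SAP still describes the full analysis, in which the diluted rate is the named primary measure for the combined period. SAP 9.2.2 sets participant counts and percentages beside the rate, but these do not correct it. The 208-only rate is free of parent time but has no switch column. The introductory sentence of SAP 16.3 says that safety outputs after an early stop follow the full plan, which could be read as keeping the combined-period tables.

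The mechanism stands, and for fatal events it needs no assumption about 207 rules. For discontinuation it stands only in part: the 207 protocol is not among the documents, and the share of stops from parent-onset AEs is unknown, so 0.69 is the full-dilution case. The column contrast rests on assumed parent-active shares, and the plan makes no inferential comparison between columns.

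The reading of SAP 16.3 does not stand. SAP 9.1, SAP 11.1, Table 9 and the opening of SAP 16 all point to the reduced package, and the Early Stop column settles each table individually. The sentence in 16.3, like its twin in 16.1, is a clerical leftover.

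**Conclusion.** No change follows, because none would alter a result. In the full analysis the discontinuation rate for the combined period would have shown at about 0.69 of its 208 at-risk value in an all-parent-active column and 0.75 to 0.82 at assumed shares of 75% to 50%. Fatal rates would have shown at 0.77 to 0.92 over the same range of shares (1 to 0.5) with exposure ending at last dose; on that denominator they are low only if the share exceeds 30/112 = 0.27. These figures assume constant hazard, 36-week completers and no parent-onset events.

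Under the recorded early termination, neither the combined-period tables nor the rates are produced, so the effect on what is reported is nil. A new time-at-risk variable and a declared departure from a protocol-stated primary rate would serve outputs that will not exist. The unstated end of patient-years is missing detail with no present consequence. Anyone who later computed a combined-period rate from these data should present it as conditional on completing 207 treatment and choose the time at risk category by category.
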